9.5.4. Laboratory Evaluations

Summaries of clinical laboratory data will be provided using descriptive statistics. No inferential statistics will be provided. Quantitative values and change from baseline in quantitative values will be summarized by dose group. Listings of all laboratory results and reference ranges will be provided.

Graded laboratory abnormalities will be defined using the grading scheme based on CTCAE (4.03). The incidence of treatment-emergent laboratory abnormalities, defined as values that increase at least one toxicity grade from baseline at any time post baseline up to and including the date of last dose of study drug, will be summarized by treatment group. If baseline data are missing, then any graded abnormality (i.e., at least a Grade 1) will be considered treatment emergent.

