1.3. Schedule of Assessments

The schedule of assessments is shown in Table 1.

Table 1. Schedule of Assessments

| Study Procedure | Screening Period | Treatment Period | | | | | | | | Follow-up Period ⁵ |
|---|---------------------------------|------------------|----|----|----|-----------------|----|------------------------------------|----------------------------------|---|
| | Study Days: D -28 to D -1 | D1 ¹ | D2 | D3 | D4 | D5 ¹ | D6 | D10 ² (Cycle 1 only) | D22 (last cycle) ⁴ | 28 (±5) days post last dose or at early termination |
| | Study Visits: V1 | V2 | V3 | V4 | V5 | V6 | V7 | V8 | | |
| Informed consent | X | | | | | | | | | |
| Inclusion/exclusion criteria | X | X | | | | | | | | |
| ECOG Performance Status | X | | | | | | | | | X |
| Medical history | X | | | | | | | | | |
| HIV and hepatitis screening ⁶ | X | | | | | | | | | |
| Pregnancy test ⁷ | X | X | | | | | | | | |
| Cancer evaluation ⁸ | X | X | | | | | | | | |
| CT or MRI | X | | | | | | | | | |
| MUGA or ECHO | X | | | | | | | | | |
| Hematology ⁹ | X | X | | | X | | | X | X | X |
| Clinical chemistry ¹⁰ | X | X | | | X | | | X | X | X |
| Thyroid panel ¹¹ | X | X | | | | | | | | |
| Coagulation test ¹² | X | X | | | | | | | | |
| Urinalysis ¹³ | X | X | | | | X | | X | X | X |
| Full physical exam ¹⁴ | X | | | | | | | | | X |
| Assess for physical symptoms/toxicities ¹⁵ | | X | X | X | X | X | X | X | X | |
| Ophthalmologic exam ¹⁵ | X | | | | | | | | | X |
| Vital signs ¹⁶ | X | X | X | X | X | X | X | X | X | X |
| ECG ¹⁷ | X | X | | | | X | | | | X |
| Start 24- hour Holter monitor ¹⁸ | | X | | | | | | | | |

| Study Procedure | Screening Period | Treatment Period | | | | | | | | Follow-up Period ⁵ |
|--|------------------|------------------|----|----|----|-----------------|----|---------------------------------|-------------------------------|---|
| | D -28 to D -1 | D1 ¹ | D2 | D3 | D4 | D5 ¹ | D6 | D10 ² (Cycle 1 only) | D22 (last cycle) ⁴ | 28 (±5) days post last dose or at early termination |
| Study Days: | V1 | V2 | V3 | V4 | V5 | V6 | V7 | V8 | | |
| Adverse events | X | X | X | X | X | X | X | X | X | X |
| Concomitant medications | X | X | X | X | X | X | X | X | X | X |
| PK blood samples ¹⁹ | | X | X | | | X | X | | | |
| PK urine samples ²⁰ | | X | X | | | X | X | | | |
| β glucuronidase urine sample ²¹ | | X | | | | X | | | | |
| Biomarker blood sample ²² | | X | | | | X | | | X | X |
| Body surface area ²³ | | X | | | | | | | | |

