| CPX-POM infusions ²⁴ | | X | X | X | X | X | | | | |

Abbreviations: ALP = alkaline phosphatase; ALT = alanine aminotransferase; aPTT = activated partial thromboplastin time; AST = aspartate aminotransferase; BSA = body surface area; BUN = blood urea nitrogen; CPX-POM = ciclopirox phosphoryloxymethyl ester; CT = computed tomography; D = day; ECG = electrocardiogram; ECOG = Eastern Cooperative Oncology Group; EDTA = ethylenediamine tetraacetic acid; eGFR = estimated glomerular filtration rate; GGT = gamma glutamyl transferase; HIV = human immunodeficiency virus; IV = intravenous; MUGA = multi-gated acquisition; MRI = magnetic resonance imaging; PBMC = peripheral blood mononuclear cell; PD = pharmacodynamic; PK = pharmacokinetic; PT = prothrombin time; RBC = red blood cell; T3 = triiodothyronine; T4 = thyroxine; TSH = thyroid stimulating hormone; V = visit; WBC = white blood cell.

1. On Days 1 and 5 of Cycle 1, patients will be required to stay at the clinical research unit for at least 12 hours for PK sampling and other assessments. If patients are unable or unwilling to attend the required 12 hours of clinic visitation required for steady-state PK sampling on Day 5 of Cycle 1, the steady-state PK sampling may be postponed to Day 5 of Cycle 2. To shorten the duration of the Cycle 1, Day 1 visit, if needed, the safety laboratory blood samples required for this visit may be drawn up to 3 days before Day 1.
2. The Day 10 (Visit 8) study visit will only be required during Cycle 1.
3. After cycle 1; visit windows can be considered on a case by case basis due to events such as holidays; Cycle 1 needs to occur without visit windows. D6 can occur +2 calendar days for cycles after Cycle 1 is completed.
4. If final treatment cycle, patient returns for assessments on Day 22. If additional cycles are planned, patient skips this visit and restarts schedule at Day 1 (except for PK). Patients may continue to receive cycles of CPX-POM until progression of disease, intolerable toxicity occurs, or another withdrawal criterion applies.

5. The Follow-up visit will occur 28±5 days after the last dose of CPX-POM administered during the last treatment cycle. Or, in the event that a patient discontinues from the study prematurely, the site will make every effort to perform the assessments listed for this study visit.
6. Hepatitis screening will include tests for Hepatitis A, Hepatitis B, and Hepatitis C.

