6.1.4. Dosage and Administration

CPX-POM will be administered as an IV infusion once daily on Days 1-5 of each 21-day treatment cycle. CPX-POM will be added to a 100 mL piggyback bag of 0.9% sodium chloride solution and infused over a 10-minute period. The initial dose for the first patient enrolled (i.e., Cohort 1) will be 30 mg/m².

At baseline, the body surface area (BSA) will be calculated by the Dubois method using Screening height and baseline weight measurements. The baseline BSA is to be used to determine the patient's study drug dose. Thereafter, BSA is to be recalculated on Day 1 of every other treatment cycle, starting with Cycle 3, and the patient's study drug dose adjusted accordingly.

$$\text{Dubois Formula: } \text{BSA} = 0.007184 \times W^{0.425} \times H^{0.725}$$

The dose escalation procedure is described in Section 4, and further details and example doses are shown in Section 4.2.

After completion of Cycle 1 for the first 4 to 6 patients, the SRC will review safety, PK, and PD data to determine if any changes to the dosing schedule are indicated (e.g., adding an additional 5 days of dosing to each treatment cycle).

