6.1.5. Dose Modifications

If a patient develops a DLT, CPX-POM dosing should be discontinued until the toxicity is resolved (see definition of a DLT in Section 4). If the toxicity resolves to at least Grade 1, treatment may be re-initiated and the dose of CPX-POM should be reduced by one dose level. If a patient has a second episode of the same DLT despite dose reduction, they should be permanently discontinued from study.

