7. DISCONTINUATION OF STUDY INTERVENTION AND PATIENT DISCONTINUATION/WITHDRAWAL

7.1. Discontinuation of Study Treatment

Treatment should be discontinued for a DLT until the toxicity is resolved. If treatment is reinitiated, then the dose of CPX-POM should be reduced as described in Section 6.1.5. If a patient has a second episode of the same DLT despite dose reduction, he or she should be removed from study as outlined in Table 1. Schedule of Assessments (complete D22 and the Early Termination Visit).

In the event of discontinuation of CPX-POM, every effort should be made to complete the assessments that are scheduled for the Follow-up/Early Termination visit. See the Schedule of Assessments (Table 1) for data to be collected at the time of early termination.

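### The laboratory incidence in Protocol 9.5.4 stops at the last dose, so it omits final-cycle Day 22 and Follow-up results, and Day 10 for patients not dosed again after Cycle 1

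*Protocol*

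**What the plan says.** Protocol 9.5.4 summarizes, by treatment group, the incidence of laboratory values that worsen by one or more CTCAE grades over baseline. The counting window is "at any time post baseline up to and including the date of last dose of study drug". No allowance is made for the period after dosing.

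Dosing and sampling are set out as follows:

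- Protocol 6.1.4: "CPX-POM will be administered as an IV infusion once daily on Days 1-5 of each 21-day treatment cycle".
- Table 1 schedules hematology and chemistry at Screening, Day 1, Day 4, Day 10, Day 22 and Follow-up. Urinalysis has Day 5 in place of Day 4.
- Table 1, footnote 2: "The Day 10 (Visit 8) study visit will only be required during Cycle 1".
- Table 1, footnote 4: Day 22 is attended only in a patient's final cycle. A patient who continues goes to Day 1 of the next cycle instead.
- Table 1, footnote 5: "The Follow-up visit will occur 28±5 days after the last dose of CPX-POM administered during the last treatment cycle". The column heading adds the early-termination case: "28 (±5) days post last dose or at early termination".

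The supplied SAP consists of table and listing shells. None of them restates the 9.5.4 definition. Table 14.3-2.1.4 (worst grade per patient) refers to *on-study* grades and Table 14.3-2.1.5 (baseline grade by worst grade) to *on-treatment* grades. The shells define neither term.

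**The concern.** With five dosing days in a 21-day cycle, a window that closes at the last dose covers only the first five days of the final cycle. Day 22 of that cycle and Follow-up come after the last dose by construction. Day 10 also falls outside for a patient who receives no dose after Cycle 1.

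Two consequences follow. First, a grade increase first seen at one of these visits is missing from the incidence. Second, the same Day 10 result counts for a patient who is dosed in Cycle 2 and does not count for one who is not, so inclusion depends on something that happens after the measurement.

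The window also differs from the protocol's other safety windows. DLT evaluation requires safety follow-up through Day 22 or Cycle 2 Day 1 (4.1). AEs are collected through Follow-up (8.2.1.2). The treatment-emergent AE definition has a start date but no end date (9.5.3). As an illustration, a drug-related Grade 4 platelet count first seen on Cycle 1 Day 10, in a patient never dosed again, meets a DLT criterion in 4.1. Under 9.5.4 it is not a treatment-emergent laboratory abnormality.

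**Working it through.** The plan gives no figure to reproduce, so the check is a count of visits against the window.

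**Inputs.** Doses on Days 1-5 of 21 (6.1.4); draw days from Table 1 and its footnotes 2, 4 and 5; window end from 9.5.4. Cycle 1 Day 1 is treated as baseline, in line with the SAP shells.

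**Formulas.** For a patient with *n* cycles and all five doses in the last one:

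- last dose on study day 21(*n* − 1) + 5;
- final-cycle Day 22 on study day 21(*n* − 1) + 22;
- Follow-up on the last-dose day + 28 ± 5;
- post-baseline hematology/chemistry draws: Day 4 of each cycle (*n*), Day 10 of Cycle 1 (1), Day 1 of Cycles 2 to *n* (*n* − 1), final-cycle Day 22 (1) and Follow-up (1), a total of 2*n* + 2.

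A draw counts if its study day is on or before the last-dose day.

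| Cycles | Last dose (study day) | Final-cycle Day 22 | Follow-up (range) | Draws counted | Draws excluded |
|---|---|---|---|---|---|
| 1 | 5 | 22 | 33 (28-38) | 1 of 4 | 3 of 4: Day 10, Day 22, Follow-up |
| 2 | 26 | 43 | 54 (49-59) | 4 of 6 | 2 of 6: Day 22, Follow-up |
| 3 | 47 | 64 | 75 (70-80) | 6 of 8 | 2 of 8: Day 22, Follow-up |

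Urinalysis gives the same counts, because Day 5 replaces Day 4 and falls on the last-dose day. Coagulation and thyroid tests are scheduled only at Screening and Day 1, so they have no scheduled draw after the last dose.

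**Earlier stop.** If Cycle 1 dosing ends on Day 1, 2 or 3 and is never resumed, Day 4 is lost as well and 4 of 4 hematology/chemistry draws are excluded. This is conditional, since Protocol 6.1.5 says "If the toxicity resolves to at least Grade 1, treatment may be re-initiated", and a later dose reopens the window.

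**Changed schedule.** The Safety Review Committee may change the dosing schedule, for example by adding five dosing days per cycle (6.1.4). The documents do not say which days. If the last dose then fell on or after Day 10, Day 10 would count and the one-cycle exclusion would drop from 3 of 4 to 2 of 4. Follow-up at 28 ± 5 days after the last dose would still be outside.

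**With the window run through Follow-up**, 4 of 4, 6 of 6 and 8 of 8 draws count.

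**The case against.** The strongest reply is that little is lost. The summary is descriptive, and 9.5.4 rules out inferential statistics. Late values remain in the listings and in the SAP by-visit tables (14.3-2.1.1 to 14.3-2.1.3), which include Day 22 and the follow-up visit. Clinically significant abnormalities are also recorded as AEs (8.2.3.6) and enter AE tables that have no end date. All of this stands, and it limits the point.

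A reader might infer that laboratory toxicity severe enough to end treatment disappears from the report. The documents do not support that. Such an abnormality would ordinarily be clinically significant and so be recorded as an AE, and 9.5.1 separately summarizes DLTs and Grade 2 or higher AEs by dose group.

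A reader might also infer that a late increase can be found only in listings and by-visit tables. That is too strong. Table 14.3-2.1.5 is graded and baseline-adjusted, and Table 14.3-2.1.4 reports worst grade. Either may include late values, or may adopt the 9.5.4 cut-off. The shells do not settle it.

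Finally, Protocol Section 9 describes itself as a summary to be finalized in the SAP, and the shell for Listing 16.2.8-5 refers to SAP text that is not among the supplied pages. That text might define the window differently. No visible passage does, and the 9.5.4 wording is explicit.

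**Conclusion.** The point holds for the 9.5.4 incidence as written. On the base schedule it excludes final-cycle Day 22 and Follow-up for every patient who has those visits, apart from an early-termination visit held on the last-dose date. It excludes Day 10 only for a patient not dosed again after Cycle 1. The incidence can be understated, and it depends in part on later dosing.

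The practical effect falls mainly on late grade increases not judged clinically significant. How often these occur cannot be read from the documents. For scale only, one uncounted patient moves a dose group's incidence by 100/3 = 33.3 points in a cohort of three and 100/6 = 16.7 points in a cohort of six. A patient already counted for the same parameter at an earlier draw changes nothing. It would be wrong to read this as a flaw in dose finding, because DLT assessment has its own window through Day 22 and the MTD rule does not use the 9.5.4 incidence.

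The draw counts assume dosing on Days 1-5, all five doses given in the last cycle, no dose after the stated last one, and scheduled draws only. The finding should be fixed. Confidence is high for the protocol wording and lower for its effect on the final tables, given the undefined SAP terms.

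**What to change.** In Protocol 9.5.4 keep the opening of "at any time post baseline up to and including the date of last dose of study drug" and replace the part from *up to* onward with: *through the Follow-up visit (28 ± 5 days after the last dose, or at early termination)*.

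In the SAP, define *on-study* in Table 14.3-2.1.4 and *on-treatment* in Table 14.3-2.1.5 by that same window. Do the same in the chemistry versions (14.3-2.2.4 and 14.3-2.2.5) and the urinalysis versions (14.3-2.5.4 and 14.3-2.5.5). Naming the tables matters because no visible shell is titled as the 9.5.4 incidence, so editing the protocol alone might change no output.

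Optionally, flag values drawn after documented progression or after the start of another anticancer therapy.

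The cost is one phrase in the protocol, a window definition in six table shells and, if the flag is used, a small programming step. All the samples are already scheduled. The downside is that rates may look slightly less favourable, and some late values may reflect progression or later therapy rather than study drug.

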9.5.5. Other Safety Evaluations

Physical examination, ECG (including Holter Monitor), ophthalmologic examination, and vital signs data will be summarized by dose group and overall. Concomitant medications will be coded using the World Health Organization Drug Dictionary and listed by dose group.

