15. Ophthalmology evaluations will be conducted at least on Day 1 and at Follow-up by a qualified ophthalmologist and will include visual acuity, pupil exam, confrontation visual field, extraocular motility and alignment, interior slit lamp examination, and dilated fundus examination of the retina. Additional ophthalmology evaluations may be performed at any other time, if indicated, as determined by the investigator.
16. Vital signs will be measured before any blood draws scheduled for the same time point. Vital signs will include blood pressure, respiratory rate, pulse, oxygen saturation, and temperature. On Days 1 and 5, vital signs will be measured at pre-dose and at 6-hour intervals post-dose.
17. At Screening, 12-lead ECGs will be performed in triplicate, with each measurement separated by 2 minutes. The average of the 3 screening ECGs will be used to calculate QTc interval to determine study eligibility. Thereafter, single 12-lead ECGs will be performed for all patients prior to drug administration on Days 1 and 5 of Cycle 1; on Day 1 of each subsequent treatment cycle; and at the Final Study visit.
18. **Cycle 1:** Starting on Day 1 of Cycle 1, digital Holter monitoring will be performed from 45 minutes pre-dose through 24 hours post-dose. ECG extractions of the continuous Holter recordings will be performed at 45, 30, and 15 minutes pre-dose and at specific post-dose time points

coinciding with the serial blood sampling time points for pharmacokinetics. Patients will be instructed to assume a supine position 5-10 minutes prior to each serial blood sampling time point and remain supine throughout the 5-minute ECG extraction period just prior to serial blood sample collection. During the 24-hour Holter monitoring period, a 12-lead ECG tracing may be printed out at any time while the patient is in the clinic at the discretion of the investigator. If for any reason Holter monitoring is not performed in conjunction with the PK sampling on Day 1 or the tracings are of poor quality, Holter monitoring may be performed in conjunction with the PK sampling on Day 5.

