19. **Cycle 1:** Serial, 3-mL blood samples will be taken for determination of plasma CPX-POM and metabolites concentrations during Cycle 1 at 0.25, 0.5, 1.0, 1.5, 2.0, 3.0, 4.0, 5.0, 6.0, 8.0, 10.0, 12.0, and 24.0 hours following completion of the 10-minute IV infusion on Day 1 and on Day 5. Each PK sample should be collected as close as possible to the planned time. The 12.0 hour collection can have a +/- 1-hour window (collect within 11 to 13 hours) and the exact time must be recorded. The actual date and time of each blood sample collection will be accurately recorded.
20. **Cycle 1:** Complete 24-hour urine samples for determination of CPX-POM and metabolites concentrations, and measurement of urine volume will be obtained from each patient in urine collection and storage containers during Cycle 1. A sample will be taken at pre-dose on Day 1, and complete urine samples will be collected at 0-12 and 12-24 hour collection intervals post-dose on Days 1 and 5. The 12 hour collection can have a +/- 1-hour window (collect within 11 to 13 hours) and the exact time must be recorded.
21. **Cycle 1:** Urine β -glucuronidase activity will be determined in the complete 24-hour urine samples collected on Day 1 and Day 5 of Cycle 1.
22. 7-mL blood samples will be obtained in EDTA-containing blood collection tubes at pre-dose on Day 1 and Day 5 of each treatment cycle, and on Day 22 of the last treatment cycle. Plasma and buffy coat (PBMCs) will be isolated, transferred to storage tubes, and stored frozen.
23. BSA will be calculated by the site personnel using the Dubois method of calculation using screening height and baseline weight measurements. BSA is to be recalculated before study drug administration on Day 1 of every other treatment cycle, starting with Cycle 3 and the patient's study drug dose adjusted accordingly.
24. CPX-POM infusions will be administered once every 24 hours as 10-minute IV infusions on Days 1-5 of each 21-day treatment cycle. After completion of Cycle 1 for the first 4 to 6 patients, the SRC will review safety, PK, and PD data to determine if any changes to the dosing schedule are indicated (e.g., adding an additional 5 days of dosing to each treatment cycle).

GLOSSARY OF ABBREVIATIONS AND DEFINITION OF TERMS

| | |
|----------------------|---|
| AE | adverse event |
| ALT | alanine aminotransferase |
| ANC | absolute neutrophil count |
| aPTT | activated partial thromboplastin time |
| AST | aspartate aminotransferase |

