8.2.3.5. Electrocardiograms and Holter Monitoring

At Screening, 12-lead ECGs will be performed in triplicate, with each measurement separated by 2 minutes. The average of the 3 screening ECGs will be used to calculate QTc

and QTcF (Fridericia's formula):
$$QTc = \frac{QT}{\sqrt[3]{RR}}$$

to determine study eligibility. Thereafter, single 12-lead ECGs will be performed at the dates and times indicated in the Schedule of Assessments (Table 1).

On Day 1 of Cycle 1, digital Holter monitoring will be performed from 45 minutes pre-dose through 24 hours post-dose in order to examine any potential QTc changes and relate those, if present, to simultaneously obtained blood samples for plasma drug and/or metabolite concentration determination. ECG extractions of the continuous Holter recordings will be performed at 45, 30, and 15 minutes pre-dose and at specific post-dose time points coinciding with the serial blood sampling time points for PK. Patients will be instructed to assume a supine position 5 to 10 minutes prior to each serial blood sampling time point and remain supine throughout the 5-minute ECG extraction period just prior to serial blood sample collection. During the 24-hour Holter monitoring period, a 12-lead ECG tracing may be printed out at any time while the patient is in the clinic at the discretion of the investigator.

If for any reason Holter monitoring is not performed in conjunction with the PK sampling on Day 1 or the tracings are of poor quality, Holter monitoring may be performed in conjunction with the PK sampling on Day 5.

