Normal	XX (XXX.X)	XX (XXX.X)	XX (XXX.X)	XX (XXX.X)	XX (XXX.X)	XX (XXX.X)	XX (XXX.X)
Abnormal, NCS	XX (XXX.X)	XX (XXX.X)	XX (XXX.X)	XX (XXX.X)	XX (XXX.X)	XX (XXX.X)	XX (XXX.X)
Abnormal, CS	XX (XXX.X)	XX (XXX.X)	XX (XXX.X)	XX (XXX.X)	XX (XXX.X)	XX (XXX.X)	XX (XXX.X)

<for Cycle 2 to last-1 cycle, repeat for Day 1 visit>
 <for last cycle, repeat for Day 1 visit and Day 28 follow-up visit>
 <repeat for PR interval and QRS interval>

* Denominator for the percentages.

[a] Baseline was the last value/result of assessment prior to or on day of first study treatment.

CS = Clinically Significant; NCS = Not Clinically Significant.

Program: (Program name.sas) (run on: DDMMYYYY HH:MM)

Filename: (Specify file name.rtf)

Table 14.3-4.2 - Summary of Abnormal ECG Intervals
 (Safety Population)

Parameter/ Visit/ Category	CPX-POM 30 mg/m ² N=1	CPX-POM [D2] mg/m ² N=X	CPX-POM [D3] mg/m ² N=X	CPX-POM [D4] mg/m ² N=X	CPX-POM [D5] mg/m ² N=X	CPX-POM [D6] mg/m ² N=X	CPX-POM [D7] mg/m ² N=X
QTcB interval (msec)							
Baseline [a] *	XX	XX	XX	XX	XX	XX	XX
> 450 msec	XX (XXX.X)	XX (XXX.X)	XX (XXX.X)	XX (XXX.X)	XX (XXX.X)	XX (XXX.X)	XX (XXX.X)
> 480 msec	XX (XXX.X)	XX (XXX.X)	XX (XXX.X)	XX (XXX.X)	XX (XXX.X)	XX (XXX.X)	XX (XXX.X)
> 500 msec	XX (XXX.X)	XX (XXX.X)	XX (XXX.X)	XX (XXX.X)	XX (XXX.X)	XX (XXX.X)	XX (XXX.X)
Cycle 1-Day 5 *	XX	XX	XX	XX	XX	XX	XX
> 450 msec	XX (XXX.X)	XX (XXX.X)	XX (XXX.X)	XX (XXX.X)	XX (XXX.X)	XX (XXX.X)	XX (XXX.X)
> 480 msec	XX (XXX.X)	XX (XXX.X)	XX (XXX.X)	XX (XXX.X)	XX (XXX.X)	XX (XXX.X)	XX (XXX.X)
> 500 msec	XX (XXX.X)	XX (XXX.X)	XX (XXX.X)	XX (XXX.X)	XX (XXX.X)	XX (XXX.X)	XX (XXX.X)
Change from Baseline to Cycle 1-Day 5 *	XX	XX	XX	XX	XX	XX	XX
> 30 msec	XX (XXX.X)	XX (XXX.X)	XX (XXX.X)	XX (XXX.X)	XX (XXX.X)	XX (XXX.X)	XX (XXX.X)
> 60 msec	XX (XXX.X)	XX (XXX.X)	XX (XXX.X)	XX (XXX.X)	XX (XXX.X)	XX (XXX.X)	XX (XXX.X)
<for Cycle 2 to last-1 cycle, repeat for Day 1 visit>							
<for last cycle, repeat for Day 28 follow-up visit>							
<repeat for QTcF interval>							

* Denominator for the percentages.

[a] Baseline was the last value/result of assessment prior to or on day of first study treatment.

CS = Clinically Significant; NCS = Not Clinically Significant.

Program: (Program name.sas) (run on: DDMMYYYY HH:MM)

Filename: (Specify file name.rtf)

PROGRAMMING NOTES: For QTcF interval, the category '> 500 msec' will be replaced by '> 500 msec (CS)' and the category '> 60 msec' will be replaced by '> 60 msec (CS)'.

Sponsor: CicloMed

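### The SAP shells specify no output for the Holter ECGs that the protocol says will be summarised, and their scheduled QTc visits fall at baseline, at trough or weeks after dosing

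*Protocol*

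**What the plan says.** **Commitment.** Protocol 9.5.5: "Physical examination, ECG (including Holter Monitor), ophthalmologic examination, and vital signs data will be summarized by dose group and overall".

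**Purpose and timing of the Holter.** Protocol 8.2.3.5 runs a 24-hour Holter on Cycle 1 Day 1 "in order to examine any potential QTc changes and relate those, if present, to simultaneously obtained blood samples". It adds that "ECG extractions of the continuous Holter recordings will be performed at 45, 30, and 15 minutes pre-dose and at specific post-dose time points", and these are to coincide with PK sampling. The recording may be done on Day 5 if the Day 1 recording is missing or of poor quality. Table 1 footnote 19 gives the PK times: "0.25, 0.5, 1.0, 1.5, 2.0, 3.0, 4.0, 5.0, 6.0, 8.0, 10.0, 12.0, and 24.0 hours following completion of the 10-minute IV infusion".

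**12-lead ECGs.** After the screening triplicate, Table 1 footnote 17 says "single 12-lead ECGs will be performed for all patients prior to drug administration on Days 1 and 5 of Cycle 1", then "on Day 1 of each subsequent treatment cycle; and at the Final Study visit".

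**SAP shells.** The QTc page of Table 14.3-4.2 counts QTcB and QTcF above 450, 480 and 500 msec, and rises above 30 and 60 msec. Its only Cycle 1 change row is "Change from Baseline to Cycle 1-Day 5". It then repeats for Day 1 from Cycle 2 to the last cycle but one, and for the Day 28 follow-up. Listing 16.2.8-6 follows a similar set of visits and has a date column but no clock time. Table 14.3-4.1 is a copy of the hematology shell with a note to include all ECG parameters.

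**The concern.** The protocol commits firmly to a Holter summary and explains why the recording is made. None of the ECG shells carries it out. The QTc outlier table, where a reader would look for a drug effect, is tied to visits that fall before a dose or long after one.

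A QTc effect that rises and falls within hours of a 10-minute infusion would leave no trace in the scheduled counts. The table could then look reassuring without having measured the relevant period. This is a first-in-human trial that requires QTcF below 470 msec at entry, excludes torsade risk factors and QT-prolonging drugs (Protocol 5.1 and 5.2), and labels QTcF above 500 msec or a rise above 60 msec as clinically significant (SAP Table 14.3-4.2).

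**Working it through.** The plan gives no figure to reproduce. The check sets the QTc visits in the shells against the protocol's ECG and dosing schedules.

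**Dosing.** Table 1 footnote 24: "CPX-POM infusions will be administered once every 24 hours as 10-minute IV infusions on Days 1-5 of each 21-day treatment cycle".

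**Time since the last dose at each QTc visit in Table 14.3-4.2**

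| SAP visit | Matching 12-lead ECG (Table 1 footnote 17) | Time since last dose |
|---|---|---|
| Baseline | Screening triplicate or pre-dose Day 1 | No prior dose |
| Cycle 1 Day 5 | Pre-dose, stated | Day 5 − Day 4 = about 24 h (trough on treatment) |
| Day 1 of later cycles | Pre-dose likely, not stated | Day 22 − Day 5 = 17 days, if the next cycle starts on time |
| Follow-up | Final visit | 28 − 5 = 23 to 28 + 5 = 33 days |

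No row is specified as post-dose on a dosing day.

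**Holter readings with no output.** There are 3 pre-dose extractions. If every PK time is used, there are 13 post-dose extractions from 0.25 to 24 h. With about 24 escalation patients (Protocol 9.1), that is up to 24 × 13 = 312 post-dose QTc values. The last time, 24 h, is itself a trough, so up to 12 per patient lie between 0.25 and 12 h.

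**Other ECG outputs.** Table 14.3-4.1 inherits Day 4, Day 10 and Day 22 from the hematology shell. Table 1 of the protocol schedules no ECG on those days, so this table does not fill the gap.

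**Baseline.** The shells take the last value before or on the day of first treatment. If Day 1 Holter values entered under that rule, a post-dose reading could become the baseline.

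**Chance effect of a per-patient maximum.** This matters for the fix. Assume no drug effect and independent normal changes with mean 0 (the SD is an assumption; the documents give none). P(at least one of 13 above 30) = 1 − (1 − p)^13, where p is the single-reading probability.

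- SD 10 msec: p = P(Z > 3) = 0.1%, rising to 1.7%.
- SD 15 msec: p = P(Z > 2) = 2.3%, rising to about 26%.

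Correlation between readings would lower both results.

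**The case against.** The strongest reply is that the SAP reviewed here consists of table, figure and listing shells. A footnote to Listing 16.2.8-5 refers out to a separate SAP text. The shells also lack other outputs that the protocol plans, such as PK parameter tables (9.6.1) and the DLT summary and logistic regression (9.5.1). A reader might infer from the shells that the Holter data will not be analysed. The documents do not support that: 9.5.5 promises a summary, and the synopsis says that exposure–ECG relationships may be explored. What can be said is that the shells specify no Holter output. The shells also take their eligibility text from Protocol Version 3.0, and whether that is the protocol text reviewed here could not be confirmed.

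Three further limits stand.

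- A reader might conclude that the tables use 12-lead ECGs only and can contain nothing post-dose. No shell names the ECG source; this is inferred from the matching visits and the missing clock time. Discretionary tracings during the Holter period, or unscheduled ECGs in the listing, could be post-dose, but they are not systematic.
- Thirteen post-dose extractions is an upper figure. The protocol refers to specific times coinciding with PK sampling and does not say that all are used.
- A reader might want to put a size on exposure at trough. The documents give no half-life. Assumed values of 4 and 12 h would leave 2^(−24/4) = 1.6% and 2^(−24/12) = 25% of peak at 24 h, a range too wide to carry weight.

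It is also fair to say that no QT signal is reported (Protocol 2 describes no ECG change in dogs over 28 days), that QTc is not a named objective, and that the DLT and MTD definitions are unaffected.

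**Conclusion.** The point holds as a gap between the protocol's commitment and the SAP shells. The scheduled QTc visits fall at baseline, about 24 hours, about 17 days and 23 to 33 days after a dose, and up to 13 post-dose Holter readings per patient have no specified table or listing. The outlier counts as laid out therefore include no scheduled value from the hours after a dose.

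This rests on reading the shells' visits as the 12-lead calendar, and on pre-dose timing for Day 1 of later cycles. For Cycle 1 Day 5, pre-dose timing is explicit. It does not rest on any assumed half-life, nor on evidence that the drug prolongs QTc. It should be corrected before the outputs are programmed. It does not threaten the primary objective.

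**What to change.** - Keep Table 14.3-4.2 and Listing 16.2.8-6 as the 12-lead outputs, and say so in their titles.
- Add a separate Holter QTcF table and listing by nominal extraction time, by dose group and overall. Use the same categories (above 450, 480 and 500 msec; rises above 30 and 60 msec) and give the maximum post-dose change per patient. State which post-dose times are extracted.
- Define the Holter baseline as the mean of the Day 1 extractions at 45, 30 and 15 minutes pre-dose.
- Flag, or show separately, patients whose Holter was moved to Day 5. Their pre-dose extractions follow four doses and are not drug-free. Use a drug-free Day 1 or screening ECG as a sensitivity baseline for them.
- Show the by-time results beside the per-patient maximum and read both descriptively, because the maximum crosses 30 msec by chance more often than one reading and there is no control group. In the single-patient cohorts a dose-group summary is one patient's values.

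The cost is programming and a data transfer. The recordings and extractions are already planned, so no new patient procedure is needed.
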